4.3.1 COVID-19 pandemic-related missing data

Efficacy Variables

Data collected during an active COVID-19 infection (confirmed by a positive SARS-CoV-2 test by PCR or an AE confirming COVID-19 infection) will be used in the primary efficacy analysis as they are not expected to be biased.

Treatment interruptions and additional pandemic-related reasons for treatment interruption will be collected and the time of the interruption will be subtracted from the exposure duration (for details see Section 6.4.2).

The number of participants who prematurely discontinue the study and study intervention for any pandemic-related reason, as well as the reasons for premature discontinuation of study and study intervention will be reported.

The number of subjects with missed visits and the number of subjects with missing e-diary data due to COVID-19 pandemic will be displayed as well as the reason why the visit/assessment was not performed.

4.3.2 Diary data

28-day mean of ESD single items on pain

According to the ESD manual, the 28-day mean of an item asking for pain can be derived if at least 15 non-missing entries² are available (i. e., the number of missing entries is < 50 %).

For calculating the primary efficacy variable only, missing entries on days during a severe COVID-19 infection as recorded on the adverse event (AE) case report form (CRF) (this means in particular that the severity is not missing) will be imputed as described in Section 6.2.1 first. Thus, the 28-day will be derived only if the number of observed and imputed daily values add up to 15 or more.

Vaginal bleeding intensity

Missing bleeding diary data will be imputed following the sponsor's instruction on the evaluation of bleeding data.

4-week mean of Endometriosis Impact Scale (EIS) single items

A 4-week average score for a respondent will only be calculated if there are at least 2 not necessarily consecutive weeks of non-missing PRO data. This is consistent with the

² By design of the eDiary (ESD and EIS), if one item is missing, all items are missing. The respondents have to select an answer for an item in order to move on to the next item.

requirement of (at least) 50 % of the data to be available for calculating the 28-day mean of the ESD single items on pain.

4.3.3 Partially missing start/stop dates

Partially missing start dates/stop dates allow for the true date lying within a certain time window that is restricted by the respective stop date/start date and the reporting date. The partially missing date/s will be imputed by the middle of the related time window in which the true date is located.

For partially/completely missing start or end dates of prior/ concomitant medication, a worst-case assumption is made, i.e. if there is the possibility that the medication was taken during the intervention period, it will be classified as “concomitant”.

This worst case assumption will be used analogously for imputing partially missing start dates and stop dates of AEs. AEs will be classified as treatment-emergent, if possible. On that basis, the duration of an AE being classified as severe will be set as long as possible. Thereafter, the duration of the classification as moderate will be maximized. Missing intensities will not be imputed.

For calculating the primary variable only, the duration of a COVID-19 infection being classified as severe will be kept to a minimum of at least 1 day to avoid unjustified imputations (see Section 4.3.2).

4.4 Interim Analyses and Data Monitoring

Two interim analysis were planned during the course of the study.

The first interim analyses was to be performed on blinded data and after approximately 50% of the study participants had completed the 12-week intervention period in order to further validate the PRO instruments used in this study.

The second interim analysis was to be performed on unblinded data once the last participant had started treatment. These interim results were to be used for planning of Phase 3 studies. No final dose decision were to be made at this point in time.

Neither of the interim analyses were planned for stopping for efficacy or futility.

The final analysis for the study will occur at the conclusion of the study. No Type-I error adjustment will be made.

As the study was terminated early, none of these interim analyses will be carried out.

4.5 Data Rules

Definition of Baseline

In general, baseline is defined as the last available measurement before start of treatment.

The 28-day baseline period for the ESD items is the last 28 days before start of treatment (e.g. -1 to -28). In case these contain less than 15 available entries, the baseline value will be given by the last 28 consecutive days before the start of treatment with at least 15 non-missing values (e.g. -2 to -29, -3 to -30, -4 to -31 and so on).

In addition, for daily measurements, if baseline and screening periods overlap, all the overlapping measurements will be considered as baseline data.

Definition of Post Baseline

In general, post baseline is defined as the first available measurement after start of treatment. Intervention period is 84 days, capturing 3 menstrual cycles of 28 days on average. As defined in Section 4.3.2, the 28-day mean of an item asking for pain can be derived if at least 15 non-missing entries are available.

Therefore, a post baseline value will be given by 28 consecutive days starting from end of treatment and counting backwards (e.g. day 84 to day 57 will be cycle 3). If a participant does not have 3 full available cycles, the count will start from the last available full cycle with at least 15 non-missing entries available (e.g. if two cycles are available, the count will start from day 56 to 29).

If a participant has 87 days of measurements, the first 3 measurements on day 1,2 and 3 will be discarded.

In addition, if a participant has more than 87 days of measurement, each data collected after day 87 will be discarded.

(Absolute change from) Baseline

To calculate the absolute change from baseline, the baseline value will be subtracted from the post-baseline value of interest, i. e.,

$$\text{Absolute change} = \text{post baseline value} - \text{baseline value.}$$

PROs data rules

If the weekly EIS questionnaire is administered less than 3 days after starting either Week 1, Week 5, 9 or 13 after start of treatment, the collected questionnaires will be counted for the previous 28-day cycle.

For example if a participant has the questionnaire pushed on day 3 after starting her treatment period, the responses will be counted as baseline.

If the monthly EQ5D questionnaire is administered less than 3 days after starting either Week 1, Week 5, 9 or 13 after start of treatment, the collected questionnaires will be counted for the previous 28-day cycle.

For example if a participant has the EQ5D questionnaire pushed on day 3 after starting her treatment period, the responses will be counted as baseline.

The above rule for the EQ5D will also apply to the follow-up cycles.

Bleeding episode

The sponsor's standard procedures defines a bleeding episode as "day(s) with bleeding/spotting of which at least one day is of intensity "light" or higher, preceded and followed by at least 2 bleed-free days" [2]. Bleeding episodes will be derived from the ESD.

An episode is left censored if it starts at or before day 2 of the diary. Left censored episodes are expected to count to the previous cycle / reference period and are therefore ignored in all

episode related evaluations. Bleeding / spotting days of left censored episodes are evaluated in all day related evaluations as they would for not left censored episodes.

Likewise, for bleeding/spotting on the second last or last study day, the unobservable following two bleed-free days will be assumed to be given.

The reason for this is that each bleeding/spotting episode, spotting only episode, or bleeding free interval is attributed to the reference period in which it begins.

In addition, if a participant does not experience any bleeding days during the 28-day cycle, the observations collected will not be assessed for the dysmenorrhea endpoint.

Numerical coding of ESD values when response is not expected by design

The ESD device is programmed such that items 2 (worst constant pain) and 3 (worst short-term pain) are not administered if the participant reports no pain for item 1 (pain at its worst). Based on the logical relation of the questions, the values for items 2 and 3 will be set to 0 when item 1 = 0.

COVID-19 infection

The start of an active COVID-19 infection is defined as the date of the first positive SARS-CoV-2 RNA test or the start date of the AE confirming the COVID-19 infection, whichever is earliest. For participants with documented vaccination against COVID-19 during the study, positive serology IgG tests post vaccination will not be considered an active COVID-19 infection.

For the relevant MedDRA preferred terms see Appendix 3 [3]

The distinguishment of P2X3 related taste AEs from COVID-19 related smell/taste symptoms will be done by individual patient review based on the details of smell/taste disturbance assessments, the SARS-CoV-2/serology IgG test results, the AEs confirming COVID-19 and the timing information.

Rescue Medication

Ibuprofen rescue medication will be reported as 400mg. For the country in which this is collected as 200mg (Japan and USA), the number of tablets collected will be divided by 2.

Repeated measurements at the same visit

If more than one measurement flagged as valid for analysis is available for a given visit, the valid measurement closest to the start of treatment will be used in the data summaries. This is the last valid measurement before and the first valid measurement after the start of treatment visit. In the data listings, all observations will be presented.

Data Rules for laboratory measurements

For lab values reported as “<x”, “<x.x”, “<x.xx” or etc. the value for analysis used will be derived by “x/2”, “x.x/2”, “x.xx/2” etc. For lab values reported as “>x”, “>x.x”, “>x.xx” or etc. the value for analysis used will be derived by increasing the last digit by 1.

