8.1.1.2 Endometriosis Impact Scale (EIS)

- EIS version 5.0 is a multi-item PRO instrument designed to assess the impact of endometriosis symptoms on the patients' lives.
- EIS was used in a validation study (22) and subsequently in a treatment study with an aromatase inhibitor (17). Regarding the rationale of developing the EIS, see Gerlinger et al. 2012 (24).
- The EIS will be completed by the study participant once a week (between 18:00 and 24:00), when she is to reflect on her experiences during the past 7 days. In case a study participant misses to enter data, EIS will be available for data entry the next day.
- Participants are to reflect on the effect of endometriosis pain on their daily lives during the past 7 days. Participants will be asked to describe impacts on:
 - o physical activities (physical subscale; contains 7 single items)
 - o emotional effect (emotional subscale; contains 7 single items)
 - o sexual activities (sexual activities subscale; contains 3 single items)
 - o ability to concentrate
 - o ability to sleep
 - household activities
 - o paid work or study
 - o social and leisure activities
- Participants will be asked to rate on a 5- to 6-point scale (6-point scales are used for items which allow for the rating of a "does not apply" option) where 0 represents "does not apply", 1 represents "not at all" and 5 represents "extremely".

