8.1.1.6 EuroQoL 5-dimension 5-level (EQ-5D-5L)

The EQ-5D-5L is a self-administered preference-based generic measure of health status which includes five dimensions: mobility, self-care, usual activities, pain/discomfort, and anxiety/depression (27). Patients provide a rating for each question on a five-level Likert scale: having no problems, having slight problems, having moderate problems, having severe problems and being unable to do/having extreme problems. In addition, patients are asked to self-rate their own health today on a vertical 0-100 unit visual analogue scale (VAS), with 0 corresponding to "the worst health you can imagine", and 100 corresponding to "the best health you can imagine".

EQ-5D-5L will be collected on eDiary and programmed after EIS data collection weekly during screening phase before treatment and monthly (every 4 weeks) during the treatment phase and follow up.

The reported data will be analyzed descriptively. The utility analyses based on collected EQ-5D-5L data are planned to be conducted in separate post-hoc analyses.

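### EQ-5D-5L forms completed after the first dose, up to day 3, are counted as baseline although pre-dose forms are planned weekly

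*SAP*

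**What the plan says.** The general rule in SAP 4.5 is: "In general, baseline is defined as the last available measurement before start of treatment". The questionnaire rules later in the same section depart from it. The condition reads: "If the monthly EQ5D questionnaire is administered less than 3 days after starting either Week 1, Week 5, 9 or 13". A form that meets it goes to the preceding 28-day cycle. The worked example for Week 1 is that "if a participant has the EQ5D questionnaire pushed on day 3 after starting her treatment period, the responses will be counted as baseline". A further sentence extends the rule: "The above rule for the EQ5D will also apply to the follow-up cycles". The weekly EIS gets the same rule in nearly the same words.

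The two instruments look back over different periods. For the EIS, Protocol 8.1.1.2 has the participant answer "when she is to reflect on her experiences during the past 7 days". For the EQ-5D-5L visual analogue scale, Protocol 8.1.1.6 says that "patients are asked to self-rate their own health today". It gives no recall period for the five dimensions.

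On timing, Protocol 8.1.1.6 plans EQ-5D-5L weekly before treatment and every 4 weeks afterwards, programmed to follow the EIS. The Schedule of Activities puts the first dose at the site at Visit 2 (day 1). SAP 6.2.3.3 uses the EQ-5D baseline for shift tables and for changes in the visual analogue scale, by treatment. SAP section 7 explains the data-rule update by questionnaires having been sent out of step with the start of treatment; it does not mention recall periods.

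**The concern.** A baseline is meant to describe the participant before treatment. For a 7-day-recall instrument, a form from the first days of treatment still describes mostly untreated days, so moving it back is defensible. A rating of health on the day itself has no such look-back: on day 2 or 3 it describes a treated day only. If that value becomes the baseline, whatever the treatment has already done, good or bad, is subtracted from every later change for that participant.

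The SAP also does not say whether the early form replaces an existing pre-dose form, is used only when there is none, or is combined with the others. Two programmers could derive different baselines from the same data. At stake are the descriptive EQ-5D-5L tables and anything later built on the same baseline variable.

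**Working it through.** The plan states no figure on this point, so there is none to reproduce.

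**1. The window.** With day 1 as the day of first dose, day d lies d − 1 days after the start of Week 1. Days 1, 2, 3 and 4 give 0, 1, 2 and 3. The limit of less than 3 days therefore takes in days 1 to 3 and excludes day 4. The day 3 example fits.

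**2. Treatment taken by then.** Assume a morning first dose. By the evening of day d, a participant on twice-daily tablets has taken 2d − 1 doses before the evening dose and 2d after it: 3–4 on day 2 and 5–6 on day 3. An elagolix participant has taken d doses: 2 and 3.

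**3. What each form describes.** A day 3 EIS form covers 7 days, of which at most 3 are on treatment, so at least 7 − 3 = 4 are untreated. A day 2 or 3 rating on the visual analogue scale covers no untreated day. Day 1 is open: a form completed at the site before dosing is a valid baseline, one completed that evening is not.

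**4. Whether a pre-dose form should exist.** Protocol 8.1.1.6 plans weekly forms through screening before treatment. The Schedule of Activities note says weekly in the pre-intervention period, which lasts 8 to 35 days. Even on that narrower reading, 8 days contain at least one weekly slot.

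**5. How much it could matter (illustration only).** Let Δ be the true between-group difference in change, s the share of participants with an on-treatment form in the baseline, f the fraction of the final effect present at that form, and w the weight of that form in the baseline. Then:

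observed difference = Δ × (1 − w·s·f)

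The documents give none of s, f and w. With full displacement (w = 1):

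| s | f = 0 | f = 0.1 | f = 0.25 | f = 0.5 |
|---|---|---|---|---|
| 10% | 1.00 | 0.99 | 0.975 | 0.95 |
| 2/7 | 1.00 | 0.97 | 0.93 | 0.86 |
| 3/7 | 1.00 | 0.96 | 0.89 | 0.79 |

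The shares 2/7 and 3/7 assume sending days spread evenly over the week, falling on days 2–3 or days 1–3.

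- If the pre-dose form is kept, w = 0 and the factor is 1.00 throughout.
- If four or five forms were averaged, w is 1/4 or 1/5, and the most extreme cell becomes 1 − 0.214/4 = 0.95 or 1 − 0.214/5 = 0.96.
- If the early effect runs against the final one, f is negative and the difference is inflated. For f = −0.25 and s = 2/7, the factor is 1 + 0.071 = 1.07.

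**6. The other time points.** Week 13 starts on day 12 × 7 + 1 = 85, and the intervention may run to day 84 + 3 = 87. Forms from days 85 to 87 lie 0 to 2 days after that start, so the rule assigns them to the third cycle, which is where an end-of-intervention form belongs.

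**The case against.** The strongest reply is that this is a stated exception, not a slip. The baseline definition is worded as a general one, the questionnaire rule is specific, and SAP section 7 gives an operational reason. That stands as far as calling the rule a contradiction goes. It does not supply a reason for preferring an on-treatment form when a pre-dose form exists.

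Second, the rule for repeated measurements in SAP 4.5 takes the last valid value before treatment, which arguably protects the pre-dose form. But that rule works within a visit, whereas the EQ-5D rule reassigns forms between cycles, so it does not settle the matter.

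Third, EQ-5D-5L is an other endpoint, analysed descriptively, with no test attached, in a trial that was stopped early. This stands and limits the importance of the point.

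A reader might also infer more than the documents support:

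- That the 3-day limit and the day 3 example conflict. They agree once the start day is day 1.
- That all of EQ-5D-5L is a same-day measure. The protocol says so only for the visual analogue scale. The dimension items are nevertheless completed on treatment.
- That effects are diluted by roughly 9–21% (3/7 × 0.2 to 3/7 × 0.5). This assumes the share, the early effect and full displacement of the pre-dose form.
- That the bias always runs toward no effect. A transient early adverse effect would worsen the baseline and flatter later change.
- That the shift rule should go for EQ-5D-5L altogether. Step 6 shows that this would misplace end-of-intervention forms.

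**Conclusion.** The point holds in a narrow form. SAP 4.5 lets EQ-5D-5L forms completed after the first dose, up to day 3, count as baseline, although a pre-dose form should usually be available. The argument is firmest for the visual analogue scale and certain for days 2 and 3; on day 1 it depends on whether the form preceded the dose.

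Size and direction cannot be determined from the documents. The factors in the working run from no effect, through dilution to 0.79, to mild inflation, and every one rests on assumed inputs.

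The consequence is confined to descriptive EQ-5D-5L baselines, changes and shift tables. The primary endpoint is unaffected: its ESD baseline uses only days before treatment. This is a worthwhile clarification, not a threat to the trial's conclusions.

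**What to change.** Change only the Week 1 clause for EQ-5D-5L in SAP 4.5:

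- Baseline is the last form completed before the first dose.
- A form completed after the first dose, up to and including day 3, is listed but used neither as baseline nor as the Week 4 value. Otherwise a reading after about two days of treatment could stand for the whole first cycle.
- State that day 1 is the day of first dose.

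Keep the shift rule as written for the EIS, and for EQ-5D-5L at Weeks 5, 9 and 13.

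The cost is a short SAP edit and a date-time comparison in the derivation. No new data are needed. The one small downside is that a participant without any pre-dose form has no EQ-5D change from baseline; SAP 4.3 already prescribes that exclusion for missing baselines.

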4.6 Blind Review

The purpose of the blind review is to provide documentation of important deviations from the protocol and validity findings and the resulting assignment of subjects to the analysis sets (see section 5.1). This will be done according to the sponsor's applicable operational instruction [4][2]. The definition for important deviations and validity findings will be set down in the specification of assessment criteria and identification requirements before the blind review's closure.

Any changes to the statistical analysis prompted by the results of the review of study data will be documented in an amendment and, if applicable, in a supplement to this SAP before unblinding the data.

The blind review includes the continued monitoring of the number of participants who contracted COVID-19 (see Section 4.5), those otherwise affected by the pandemic (i. e., pandemic-related administrative reasons), and the related amount of missing data relevant for the primary analysis, including premature discontinuations of the study (treatment). The impact of the amount of missing data on the power of the primary analysis may be assessed by running simulations. Patient characteristics of participants with pandemic-related missing data may be compared with those of participants with observed data. The latter two analyses will not be reported.

5. Analysis Sets

5.1 Assignment of analysis sets

Final decisions regarding the assignment of participants to analysis sets will be made during the blinded review of study data and documented in the final list of important deviations, validity findings and assignment to analysis set(s) (see Section 4.6).

Enrolled

All participants who sign the Informed consent form (ICF).

Full analysis set (FAS)

All participants randomly assigned to study intervention. Participants will be analyzed according to the intervention they were randomized to.

Safety analysis set (SAF)

All participants randomly assigned to study intervention and who take at least 1 tablet of study intervention. Participants will be analyzed according to the intervention they actually received. If participants received different interventions throughout the course of the study, it will be decided in the assessment meeting on a case-by-case decision which group they will be assigned to for the final analysis. These participants will be excluded from the unblinded interim analysis.

Primary full analysis set (pFAS)

Subset of FAS, containing all participants with surgically confirmed endometriosis and outside China randomly assigned to study intervention. Participants will be analyzed according to the intervention they were randomized to.

Per protocol set (PPS)

All participants randomly assigned to study intervention, who take at least 1 tablet of study intervention, and who have no validity findings affecting efficacy.

A list of potential validity findings will be provided in a separate important deviations and validity specifications document (Assessment Criteria and Identification Requirement (ACIR)) which will be finalized before unblinding. The assignment of participants to this analysis set will be based on the assessment meetings.

The participants with missing baseline ESD item 1 (as defined in 4.5) or no valid post-baseline 28-day average of ESD item 1 will be excluded from the PPS.

Due to the repeated measurements design of the study a participant dropping out of the study may still be evaluable for efficacy and will therefore not be automatically excluded from PPS.

Participants will be analyzed according to the intervention they actually received. If participants received different interventions throughout the course of the study, they will be excluded from the PPS.

Primary Per Protocol Set (pPPS)

Subset of the PPS containing all participants in the PPS with surgically confirmed endometriosis and outside China. The analyses performed on the pPPS are chosen to be the primary one.

The PPS and pPPS will be used for all non-safety analyses and the separate pharmacodynamics analyses.

Pharmacokinetic Analysis Set (PKS)

All participants who took at least 1 dose of study drug and had at least 1 available pharmacokinetic sample.

Listing Only Set (LOS)

This set contains all screening failures. It will be used for listing purposes only.

The primary and secondary efficacy endpoints will be analyzed using the pPPS. The safety endpoints will be analyzed using the SAF. All other endpoints will be analyzed on the FAS, unless specified otherwise.

digitalBIO Analysis Set (DAS)

All participants who consented to take part in the actigraphy sub-study with any amount of actigraphy data available will be included in the Digital Measures Analysis Set. Participant may be included or excluded from particular analyses depending on the extent of available data. Participants will be analyzed according to the intervention they were randomized to.

6. Statistical Methodology

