9.3 Analysis Sets

Final decisions regarding the assignment of subjects to analysis sets defined in table 1 will be made during the review of study data and documented in the final list of important deviations, validity findings and assignment to analysis set(s).

27 JAN 2022 Page: 67 of 99

Table 9–1: Definition of the analysis sets.

Analysis set	Description		
Enrolled	All participants who signed the informed consent		
	form		
Full Analysis Set (FAS)	All randomized non-Chinese participants		
Primary full Analysis Set (pFAS)	All randomized non-Chinese participants with surgically-confirmed endometriosis		
Per Protocol Set (PPS)	All randomized non-Chinese participants without any validity findings impacting the primary efficacy variable		
Primary Per Protocol Set (pPPS)	All randomized non-Chinese participants with surgically-confirmed endometriosis and no validity finding impacting the primary efficacy variable		
Safety Analysis Set (SAF)	All participants who took at least 1 dose of study drug		
Pharmacokinetic Analysis Set (PKS)	All participants who took at least 1 dose of study drug and had at least 1 available pharmacokinetic sample		

The primary analysis will be based on the pPPS. The PPS will be used for other non-safety analyses and the separate pharmacodynamics analyses. Safety analyses will be performed on the SAF. If and only if the SAF is used, the subjects will be analyzed as treated instead of as randomized. In selected cases, the (p)FAS will be used for sensitivity analyses. PK analysis will be performed on the PKS. Data from screening failures will only be shown in separate listings.

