6.2.3 Other endpoints

The descriptive analyses of the other endpoints described in the following subsections will be based on the FAS and presented by treatment group.

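### The SAP's FAS and PPS admit Chinese women whom the protocol's FAS and PPS exclude, so the descriptive baseline, efficacy and PRO tables use a different population under the same names

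*SAP*

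**What the plan says.** Protocol Section 9.3, Table 9-1, defines the FAS as "All randomized non-Chinese participants" and the PPS as "All randomized non-Chinese participants without any validity findings impacting the primary efficacy variable". Of the uses of these sets it says: "The PPS will be used for other non-safety analyses and the separate pharmacodynamics analyses".

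SAP Section 5.1 defines the FAS as "All participants randomly assigned to study intervention" and the PPS as "All participants randomly assigned to study intervention, who take at least 1 tablet of study intervention, and who have no validity findings affecting efficacy". Neither definition mentions country. China leaves only at the next step. The pFAS is a "Subset of FAS, containing all participants with surgically confirmed endometriosis and outside China randomly assigned to study intervention", and the pPPS is a "Subset of the PPS containing all participants in the PPS with surgically confirmed endometriosis and outside China".

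The SAP then uses the wider sets as follows:

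- Section 6.1.2 reports demographics and baseline characteristics on the FAS and PPS.
- Section 6.2.3 says: "The descriptive analyses of the other endpoints described in the following subsections will be based on the FAS". Its subsections cover worst pain by 28-day window, pain on bleeding and non-bleeding days, pain in follow-up, rescue medication, EIS, EQ-5D-5L, VAS and the other PROs, by treatment group.
- The primary and secondary efficacy endpoints stay on the pPPS (Sections 5.1 and 6.2.1.1).

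SAP Section 1 says the plan is based on protocol version 3.0, amendment 2, which contains Table 9-1. Both documents say Chinese women were enrolled mainly to add data on the ESD in that population. Neither Chinese nor Japanese women are randomised to elagolix.

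**The concern.** Two governing documents give different membership to sets with the same names. Someone who reads a FAS table with the protocol in hand will assume that Chinese women are absent, and under the SAP they are present. SAP Section 7, which is headed as covering changes in the planned analysis, does not mention this.

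Two things are at stake. First, comparison with elagolix is a stated objective for the pain endpoints in these tables, and the added women can fall only in the BAY and placebo arms. Any difference between Chinese and other women therefore enters one side of that comparison. Second, the reason given for enrolling Chinese women is to learn about the ESD in that population. The SAP pools their data by treatment arm and specifies no table by country, and Section 7 records that subgroup analyses were removed. The data would be absorbed rather than shown.

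**Working it through.** **Is China really inside the SAP's FAS and PPS?** Yes. The SAP specifies the exclusion when it forms the pFAS from the FAS and the pPPS from the PPS. That step would be redundant if the parent sets already excluded China.

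**Does the choice of set matter?** SAP Section 5.1 says both that the PPS and pPPS serve all non-safety analyses and that other endpoints use the FAS. The point holds under either statement, because neither the FAS nor the PPS has a country limit.

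**Planned headcount.** Inputs from Protocol Section 9.2 and SAP Section 3.1: about 420 randomised; 28 from China; 28 from Japan with clinical diagnosis; 1:1:1:1 in those groups; 3:3:3:3:4 elsewhere, with elagolix receiving the 4. Protocol Section 5.1 caps imaging diagnosis at half of Japanese participants, so I assume another 28 surgically diagnosed, 56 from Japan in all.

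- Elsewhere: 420 − 28 − 56 = 336.
- Each blinded arm elsewhere: 336 × 3/16 = 63. Elagolix: 336 × 4/16 = 84.

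| Source | Each BAY or placebo arm | Elagolix | Total |
|---|---|---|---|
| Elsewhere | 63 | 84 | 336 |
| Japan, surgical (assumed) | 7 | 0 | 28 |
| Japan, clinical | 7 | 0 | 28 |
| China | 7 | 0 | 28 |
| **SAP FAS** | **84** | **84** | **420** |
| **Protocol FAS** | **77** | **84** | **392** |

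This reproduces the plan's figures: 5 × 84 = 420, and 63 + 7 = 70 per blinded arm for the primary analysis.

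**Share of Chinese women in the SAP FAS.** Overall 28/420 = 6.7%; each blinded arm 7/84 = 8.3%; elagolix 0/84. If the plan's 50 evaluable out of 70 applied throughout (an assumption), the PPS would be about 420 × 50/70 = 300 under the SAP and 392 × 50/70 = 280 under the protocol.

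**Effect on a reported arm mean.** If Chinese women's mean change differs by D from that of the others in the arm, the arm mean moves by D × 7/84. The documents give no value for D, so I show a range:

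- D = 0.5: 0.04 points
- D = 1: 0.08 points
- D = 2: 0.17 points

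The elagolix mean moves by 0. The four blinded arms have the same expected Chinese share, so if D is the same in each arm, BAY-placebo differences do not move in expectation.

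**Primary analysis.** I simulated the maximum-contrast test over the four candidate curves with 50 per arm, SD 2.5 and one-sided alpha 0.10. The critical value was 1.529 and power was 88.9%, 89.2%, 93.0% and 90.8%, averaging 90.5% against the stated 90%. This calculation concerns the pPPS, which excludes China in both documents, so nothing in it changes.

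**The case against.** The strongest reply is that the inclusion looks deliberate. The SAP places the China exclusion explicitly at the level of the pFAS and pPPS, and a FAS of all randomised participants is unremarkable. The protocol's sets leave Chinese women in no efficacy set at all, so nothing in Table 9-1 would report the ESD data for which they were enrolled. This stands as an explanation. It does not excuse reusing the protocol's names for different sets without saying so, and a pooled table by treatment arm still does not show the Chinese data.

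It is also fair that Section 7 lists changes between SAP versions and that SAP 1.0 is not available, so the documents do not show when the wider definition arose. The shifts are small, and the study was stopped early, so the planned 28 may not have been reached. The fix also needs care: the subject-validity overview in SAP Section 6.1.1 and medical history in Section 6.1.3 use the FAS, and narrowing it everywhere would drop randomised women from both.

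A reader might infer two stronger points that the documents do not support:

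- **That the region covariate breaks.** The adjustment contrasts Japan with the rest of the world excluding China and so has no level for Chinese women. It appears only in the primary and secondary efficacy models, which run on the pPPS. FAS efficacy tables are descriptive, and no efficacy model is specified on the FAS or PPS.
- **That restoring the protocol definition would match these tables to the primary estimand.** It would not. The protocol's own FAS and PPS keep the clinically diagnosed Japanese women, planned at 28, whom the estimand's target population excludes.

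**Conclusion.** The contradiction is real and textual. The SAP's FAS and PPS depart from the protocol version on which the SAP says it is based, and the departure is not recorded. It reaches the descriptive baseline tables and the other efficacy and PRO tables: at the plan, 28 of 420 women, 8.3% of each blinded arm and none of the elagolix arm. The effect on a blinded-arm mean is about 0.04 to 0.17 NRS points for an assumed difference of 0.5 to 2 points.

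This is a modest defect. It leaves the primary test, the secondary efficacy analysis, alpha and power untouched, and BAY-placebo differences stay balanced in expectation. What it changes is who is described in the tables, the comparison with elagolix, and whether the Chinese ESD data are visible. Japanese women are also absent from elagolix under either definition (14 of 77 per blinded arm in the protocol FAS), so restoring the restriction reduces the regional imbalance against elagolix but does not remove it.

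The figures rest on planned counts, on an assumed 28 surgically diagnosed Japanese women, and on assumed values for the difference. The documents do not say how many Chinese women were randomised. If there were none, the results are the same under either definition.

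**What to change.** In SAP Section 5.1, restore the non-Chinese restriction in the FAS and PPS used for efficacy, PRO and baseline tables. Keep the subject-validity overview (Section 6.1.1) and medical history (Section 6.1.3) on all randomised participants by naming that population there. Add one descriptive table of ESD and PRO data for Chinese participants, which serves their stated purpose.

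If the wider set is intended, give it a name other than FAS or PPS, record the departure from Table 9-1 in Section 7, and show comparisons with elagolix without Chinese participants.

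The first route costs a few words in the set definitions, two changed set references and one extra table. The second costs a renamed set, an entry in Section 7 and a restricted version of the tables that include elagolix. Neither needs new data or touches the primary or secondary analysis.
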